14.3.2.3 Patient Disposition

A detailed description of patient disposition will be provided, including a summary of the number and percentage of patients entered into the study, enrolled in the study, and treated as well as number and percentage of patients discontinuing (overall and by reason for discontinuation). A listing of all important protocol deviations will be provided.

14.3.2.4 Patient Characteristics

Demographic data are collected and reported to demonstrate that the study population represents the target patient population considered for regulatory approval.

A summary of baseline patient and disease characteristics, historical diagnoses, preexisting conditions, and prior therapies will be reported using descriptive statistics.

14.3.2.5 Concomitant Therapy

A summary of prior and concomitant medications will be reported.

14.3.2.6 Post study-Treatment-Discontinuation Therapy

The numbers and percentages of patients receiving post study-treatment-discontinuation anticancer therapies will be provided by type of therapy (surgery, radiotherapy, or systemic therapy), and by drug class and/or name, overall and by line of therapy.

14.3.2.7 Treatment Compliance

The number of cycles received, dose omissions, dose reductions, dose delays, and dose intensity will be summarized for all treated patients by treatment parts.

Study treatment compliance will be assessed as the proportion of treatment that is actually taken, relative to what is expected, after accounting for protocol-defined dose adjustments. Study treatment taken will be derived from the difference between the total number of pills dispensed and returned over the course of the patient's treatment.

15 Patient Consent and Peer Judgement

The protocol and informed consent form for this study must be approved in writing by the appropriate Institutional Review Board (IRB) prior to any patient being registered on this study. Changes to the protocol, as well as a change of principal investigator, must also be approved by the Board. Records of the Institutional Review Board review and approval of all documents pertaining to this study must be kept on file by the investigator (housed in the Clinical Trials Office) and are subject to inspection at any time during the study.

The study will be conducted in compliance with ICH guidelines and with all applicable federal (including 21 CFR parts 56 & 50), state or local laws.

16 References

Appendix 1. Abbreviations and Definitions

Term	Definition
AE	Adverse event: any untoward medical occurrence in a patient or clinical investigation patient administered a pharmaceutical product and that does not necessarily have a causal relationship with this treatment. An adverse event can therefore be any unfavorable and unintended sign (including an abnormal laboratory finding), symptom, or disease temporally associated with the use of a medicinal (investigational) product, whether or not related to the medicinal (investigational) product.
AUC_{0-tlast}, AUC_{0-∞}	area under the concentration-time curve
ATP	adenosine triphosphate
BCOP	bovine corneal opacity and permeability
BID	twice a day
CDK4	cyclin-dependent kinase-4
CI	confidence intervals
CIOMS	Council for International Organizations of Medical Sciences
CL/F	apparent clearance
C_{max}	maximum concentration
CR	complete response
CRC	colorectal cancer
CRP	Clinical research physician: Individual responsible for the medical conduct of the study. Responsibilities of the CRP may be performed by a physician, clinical research scientist, global safety physician, or other medical officer.
CTCAE	Common Terminology Criteria for Adverse Events
CTS	change in tumor size
CV_w	coefficients of variations
DDI	drug-drug interactions
DLT	dose limiting toxicity

ECG	electrocardiogram
eCRF	electronic case report form
ECG	electrocardiogram
effective method of contraception	male condom with spermicide, female condom with spermicide, diaphragm with spermicide, cervical sponge, or cervical cap with spermicide. Also see the definition of highly effective method of contraception.
EGFR	epidermal growth factor receptor
enroll	The act of assigning a patient to a treatment. Patients who are enrolled in the trial are those who have been assigned to a treatment.
enter	Patients entered into a trial are those who sign the informed consent form directly or through their legally acceptable representatives.
ERB	ethical review boards
ERK	extracellular signal regulated kinase
FDA	Food and Drug Administration
G-CSF	granulocyte-colony stimulating factor (G-CSF)
GCP	good clinical practice
GI	gastrointestinal
GnRH	gonadotropin-releasing hormone
IB	investigator's brochure
ICF	informed consent form
ICH	International Conference on Harmonisation
interim analysis	An interim analysis is an analysis of clinical trial data conducted before the final reporting database is created/locked.
investigational product	A pharmaceutical form of an active ingredient or placebo being tested or used as a reference in a clinical trial, including products already on the market when used or assembled (formulated or packaged) in a way different from the authorized form, or marketed products used for an unauthorized indication, or marketed products used to gain further information about the authorized form.
LC-MS/MS	liquid chromatography-tandem mass spectrometry
MAPK	mitogen-activated protein kinase
mCRC	metastatic colorectal cancer
MedDRA	Medical Dictionary for Regulatory Activities

MN	micronucleus
MRI	magnetic resonance imaging
MTD	maximum tolerated dose
NF1	Neurofibromin-1
NOEL	no-observed-effect level
NSCLC	non-small cell lung cancer
ORR	overall response rate
OS	overall survival
PD	pharmacodynamics
PDAC	pancreatic ductal adenocarcinoma
PET	positron emission tomography
PFS	progression free survival
PI	principal investigator
PK	pharmacokinetics
PR	partial response
QD	once daily
QTc	corrected QT interval
QW	every week
RECIST	Response Evaluation Criteria in Solid Tumors
reporting database	A point-in-time copy of the collection database. The final reporting database is used to produce the analyses and output reports for interim or final analyses of data.
re-screen	to screen a patient who was previously declared a screen failure for the same study
RTK	receptor tyrosine kinase
SAE	serious adverse event
SAP	Statistical Analysis Plan
screen	The act of determining if an individual meets minimum requirements to become part of a pool of potential candidates for participation in a clinical study.
screen failure	patient who does not meet one or more criteria required for participation in a trial

SUSARs	Suspected unexpected serious adverse reactions
t_{1/2}	half-life
TEAE	Treatment-emergent adverse event: an untoward medical occurrence that emerges during a defined treatment period, having been absent pretreatment, or worsens relative to the pretreatment state, and does not necessarily have to have a causal relationship with this treatment.
TTR	time to response
US	United States
V/F	apparent volume of distribution

Appendix 2. Study Governance, Regulatory, and Ethical Considerations

Informed Consent

Investigators are responsible for:

- ensuring that the patient understands the potential risks and benefits of participating in the study
- ensuring that informed consent is given by each patient or legal representative. This includes obtaining the appropriate signatures and dates on the ICF prior to the performance of any study procedures and prior to the administration of study treatment.
- answering any questions the patient may have throughout the study and sharing in a timely manner any new information that may be relevant to the patient's willingness to continue his or her participation in the trial.

Ethical Review

Documentation of IRB approval of the protocol and the ICF must be provided to Lilly before the study may begin at the investigative site(s). The sponsor-investigator or representative must approve the ICF, including any changes made by the IRB, before it is used at the investigative site. All ICFs must be compliant with the International Conference on Harmonisation (ICH) guideline on GCP.

The study site's IRB should be provided with the following:

- the current IB or package labeling, Patient Information Leaflet, Package Insert, or Summary of Product Characteristics and updates during the course of the study
- the ICF
- relevant curricula vitae

Regulatory Considerations

This study will be conducted in accordance with:

- consensus ethics principles derived from international ethics guidelines, including the Declaration of Helsinki and Council for International Organizations of Medical Sciences (CIOMS) International Ethical Guidelines
- applicable ICH GCP Guidelines
- applicable laws and regulations.

Investigator Information

Physicians with a specialty in oncology will participate as investigators in this clinical trial.

Protocol Signatures

Lilly's responsible medical officer will approve the protocol, confirming that, to the best of his or her knowledge, the protocol accurately describes the planned design and conduct of the study. After reading the protocol, each principal investigator will sign the protocol signature page and send a copy of the signed page to a Lilly representative.

Final Report Signature

The sponsor-investigator will sign the final clinical study report for this study, indicating agreement that, to the best of his or her knowledge, the report accurately describes the conduct and results of the study. If this investigator is unable to fulfill this function, another investigator will be chosen by Indiana University to serve as the clinical study report coordinating investigator.

The sponsor-investigator and statistician will approve the final clinical study report for this study, confirming that, to the best of his or her knowledge, the report accurately describes the conduct and results of the study.

Study and Site Closure

Discontinuation of Study Sites

Study site participation may be discontinued if Lilly, the sponsor-investigator, or the IRB of the study site judges it necessary for medical, safety, regulatory, or other reasons consistent with applicable laws, regulations, and GCP.

Discontinuation of the Study

The study will be discontinued if Lilly or the sponsor-investigator judges it necessary for medical, safety, regulatory, or other reasons consistent with applicable laws, regulations, and GC

Appendix 3. Creatinine Clearance Formula

*For serum creatinine concentration
in mg/dL:*

$$\text{CrCl} = \frac{(140 - \text{age}^a) \times (\text{wt}) \times 0.85 \text{ (if female), or } \times 1.0 \text{ (if male)}}{72 \times \text{serum creatinine (mg/dL)}} \\ \text{(mL/min)}$$

For serum creatinine concentration in $\mu\text{mol/L}$:

$$\text{CrCl} = \frac{(140 - \text{age}^a) \times (\text{wt}) \times 0.85 \text{ (if female), or } \times 1.0 \text{ (if male)}}{0.81 \times \text{serum creatinine } (\mu\text{mol/L})} \\ \text{(mL/min)}$$

^a Age in years, weight (wt) in kilograms.

Source: Cockcroft and Gault 1976.

Appendix 4. Dose Modification of LY3214996 & Abemaciclib

Neutropenia	Abemaciclib	LY3214996
≤ Grade 1/2	No change in dose.	No change in dose.
Grade 3	Hold* until ≤ Grade 2. Resume at same dose level.	No change in dose.
Recurrent Grade 3 or Grade 4	Hold* until ≤ Grade 2. Reduce by 1 dose level.	No change in dose.

*Patients requiring a delay of all protocol therapy > 3 weeks due to toxicity should go off protocol therapy.
 
NOTE: Use of prophylactic granulocyte colony stimulating factor is permitted per investigator discretion. Use of ASCO guidelines is recommended. Suspend therapy for at least 48 hours after the last dose of a blood cell growth factor was administered and until toxicity resolves to at least Grade 2.
		

Abbreviation: ASCO = American Society of Clinical Oncology

Thrombocytopenia	Abemaciclib	LY3214996
≤ Grade 1/2	No change in dose.	No change in dose.
Grade 3	Hold* until ≤ Grade 2. Resume at same dose level.	No change in dose.
Recurrent Grade 3 or Grade 4	Hold* until ≤ Grade 2. Reduce by 1 dose level.	No change in dose.

*Patients requiring a delay of all protocol therapy > 3 weeks due to toxicity should go off protocol therapy.
		

Anemia	Abemaciclib	LY3214996

Supportive transfusion is permitted after cycle 1, day 1 and future cycles for subjects who do not meet hemoglobin parameters for retreatment.
		
Hemoglobin	Abemaciclib	LY3214996
Grade 1/2	No change in dose	No change in dose.
Grade 3	Hold* until ≤ Grade 2. Resume at same dose level.	No change in dose.
Recurrent Grade 3 or Grade 4	Hold* until ≤ Grade 2. Reduce by 1 dose level.	No change in dose.
Patient requires administration of a blood cell growth factor	Suspend abemaciclib dose for at least 48 hours after the last dose of blood cell growth factor and until toxicity resolves to ≤Grade 2. Resume abemaciclib at next lower dose unless the dose was already reduced for the toxicity that led to the use of the growth factor.	No change in dose.

*Patients requiring a delay of all protocol therapy > 3 weeks due to toxicity should go off protocol therapy. Supportive transfusion is permitted after cycle 1, day 1 and future cycles for subjects who do not meet hemoglobin parameters for retreatment.
		

Recurrent in the context of dose interruptions and delays refer to the same event occurring within the next 8 weeks (as measured from the stop date of the first event). This does not include events in the same class (for example, neutropenia followed by anemia 1 month later).

As a general approach, based on the **risk/benefit balance assessment per the investigator**: for a patient who experiences a new episode of Grade 3 hematological toxicity after more than 8 weeks following the last episode of **same** Grade 3 hematological toxicity, the investigator may consider resuming the patient on the same drug dose if the patient satisfies the following conditions:

- The patient showed stable hematological counts (\leq Grade 2) during that time frame
- In the absence of any infectious sign or risk factor
- The patient is getting benefit from study treatment.

Non-Hematologic Toxicity:

Nausea**	Abemaciclib	LY3214996
\leq Grade 1	No change in dose.	No change in dose.
Grade 2	Hold* until \leq Grade 1. Resume at same dose level.	Hold* until \leq Grade 1. Resume at same dose level.
Grade 3	Hold* until \leq Grade 1. Reduce by 1 dose level.	Hold* until \leq Grade 1. Reduce by 1 dose level.
*Patients requiring a delay of all protocol therapy > 3 weeks due to toxicity should go off protocol therapy. ** After optimal anti-emetic therapy. Please refer to Section 8.6.1 . Use of prophylactic or scheduled antiemetics are recommended in future cycles for patients experiencing grade 2 or higher nausea.		

Vomiting**	Abemaciclib	LY3214996
\leq Grade 1	No change in dose.	No change in dose.
Grade 2	Hold* until \leq Grade 1. Resume at same dose level.	Hold* until \leq Grade 1. Resume at same dose level.
Grade 3	Hold* until \leq Grade 1. Reduce by 1 dose level.	Hold* until \leq Grade 1. Reduce by 1 dose level.
Grade 4	Hold* until \leq Grade 1. Reduce by 1 dose level.	Hold* until \leq Grade 1. Reduce by 1 dose level.
*Patients requiring a delay of all protocol therapy > 3 weeks due to toxicity should go off protocol therapy. ** After optimal anti-emetic therapy. Please refer to Section 8.6.1 . Use of prophylactic or scheduled antiemetics are recommended in future cycles for patients experiencing grade 2 or higher vomiting.		

Diarrhea**	Abemaciclib	LY3214996
≤ Grade 1	No change in dose.	No change in dose.
Grade 2 (1st episode)	Hold* until ≤ Grade 1. Resume at same dose level.	Hold* until ≤ Grade 1. Resume at same dose level.
Grade 2 (Persistent or recurrent following resumption of therapy)	Hold* until ≤ Grade 1. Reduce by 1 dose level.	Hold* until ≤ Grade 1. Reduce by 1 dose level.
Grade 3	Hold* until ≤ Grade 1. Reduce by 1 dose level.	Hold* until ≤ Grade 1. Reduce by 1 dose level.
Grade 4	Hold* until ≤ Grade 1. Reduce by 1 dose level.	Hold* until ≤ Grade 1. Reduce by 1 dose level.
*Patients requiring a delay of all protocol therapy > 3 weeks due to toxicity should go off protocol therapy. ** After optimal anti-diarrheal therapy. Please refer to Section 8.6.1 . Use of prophylactic or scheduled anti-diarrheals are recommended in future cycles for patients experiencing grade 2 or higher diarrhea.		

Hepatotoxicity is a known adverse drug reaction of abemaciclib. Additional information is in the IB. Should a patient experience ≥ Grade 2 increase in AST and/or ALT we recommend holding therapy with dosing guidelines below. Please follow AST, ALT, and total bilirubin at least weekly until ≤ Grade 1 prior to re-initiating study therapy. Liver function can be monitored more frequently per investigator discretion.

AST and/or ALT Elevations**	Abemaciclib	LY3214996
≤ Grade 1 (>ULN-3.0x ULN)	No change in dose.	No change in dose.
Grade 2 (>3.0-5.0 x ULN) (without increase in total bili > 2 x ULN)	Hold* until meets treatment criteria. Resume at same dose level.	Hold* until meets treatment criteria. Resume at same dose level.
Grade 2 (without increase in total bili >2 x ULN; recurrent or persistent)	Hold* until ≤ Grade 1. Reduce by 1 dose level.	Hold* until ≤ Grade 1. Reduce by 1 dose level.
Grade 3 (>5.0-20.0 x ULN) (without increase in total bili > 2 x ULN)	Hold* until ≤ Grade 1. Reduce by 1 dose level.	Hold* until ≤ Grade 1. Reduce by 1 dose level.
Grade 2 (with increase in total bili > 2x ULN)	Discontinue therapy	Discontinue therapy
Grade 3 (with increase in total bili >2 x ULN)	Discontinue therapy	Discontinue therapy
Grade 4 (>20.0 x ULN)	Discontinue therapy	Discontinue therapy
*Patients requiring a delay of all protocol therapy > 3 weeks due to toxicity should go off protocol therapy. ** Use ULN unless baseline is greater than ULN, then use baseline for grading.		

Interstitial lung disease (ILD)/pneumonitis has been identified as an adverse drug reaction for abemaciclib. Additional information is available in the IB.

Ask your patients to report any new or worsening respiratory symptoms such as cough, dyspnea, fever, and investigate and treat as per your local clinical practice, including corticosteroids as appropriate. If interstitial lung disease/pneumonitis is suspected, investigations may include imaging, such as high-resolution CT scans, bronchoalveolar lavage, and biopsy as clinically indicated. Please refer to dosing guidelines below for respiratory toxicity.

ILD/Pneumonitis	Abemaciclib	LY3214996
≤ Grade 1	No change in dose.	No change in dose.
Grade 2 (>7 days despite maximal supportive measures or recurrent)	Hold* until ≤ Grade 1 or baseline. Reduce by 1 dose level.	Hold* until ≤ Grade 1 or baseline. Resume at same dose level.
Grade 3/4	Discontinue therapy.	Discontinue therapy.
*Patients requiring a delay of all protocol therapy > 3 weeks due to toxicity should go off protocol therapy.		

Cutaneous toxicity should be managed per guidelines in [Section 8.6.1.1](#). In the event of grade 3 or higher dermatologic toxicity, hold abemaciclib and LY3214996 until dermatologic toxicity resolves to ≤ grade 2 or pre-treatment baseline. Subsequent LY3214996 treatment should be dose reduced by one dose level. Abemaciclib does not require dose reduction. Treatment may be held for up to 21 days. If the toxicity is not improved to ≤ grade 2 or pre-treatment baseline within the 21-day period, the patient will discontinue therapy. Additionally, a one level dose reduction of LY3214996 is permitted for intolerable grade 2 dermatologic toxicity, at the discretion of the treating physician. Such dose reductions should be undertaken in conjunction with management of cutaneous toxicity as described in [Section 8.6.1.1](#).

For any grade 3 or 4 toxicity, not mentioned above, the treatment should be withheld until the patient recovers to grade 1 or less toxicity. The treatment may then be resumed at one dose level reduction. For intolerable grade 2 toxicities, withhold treatment until the patient recovers, then resume treatment at a one dose level reduction. Dose reduction will be done for the drug that is most likely to have caused the toxicity. For grade 1 or tolerable grade 2 toxicities or clinically insignificant laboratory changes, no dose reduction should be made.

Dose adjustments as outlined in the table below are allowed both within a cycle and between cycles for abemaciclib. Abemaciclib must be reduced sequentially by 1 dose level.

Dose Adjustment	Oral Dose	Frequency
0	150 mg	Q12H
-1	100 mg	Q12H
-2	50 mg	Q12H

Dose adjustments as outlined in the table below are allowed both within a cycle and between cycles for LY3214996. LY3214996 must be reduced sequentially by 1 dose level.

Dose Adjustment	Oral Dose	Frequency
0	200 mg	Daily
-1	100 mg	Daily

If a patient receiving the 50-mg Q12H dose of abemaciclib requires further dose reduction, abemaciclib should be discontinued. Patients may remain on single agent treatment with LY3214996 if the investigator determines the patient is receiving clinical benefit. Dose omissions are allowed within a cycle. If a patient requires omission of more than 25% of doses during a cycle for tolerability, then treatment may continue if the investigator determines the patient is receiving clinical benefit.

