8.3 Dosage Modification

Please refer to [Appendix 4](#) for dose adjustment guidelines.

Study therapy may be held up to 3 weeks to allow sufficient time for recovery. Patients who do not recover from drug-related toxicity to \leq grade 1 within 3 weeks will be discontinued (except alopecia, fatigue, skin rash, elevated creatinine, nausea, vomiting, constipation or diarrhea that can be controlled with treatment). If a dose adjustment is made, the patient must be maintained at the reduced dose level for all remaining cycles.

For the purposes of dose modification, the investigator must first assess if the toxicity is considered at least possibly due to one of the study drugs, and must then apply the study drug-specific dose-modification guidelines accordingly. If the toxicity is not clearly attributable to either individual study drug, then the causality should be attributed to both study drugs. Dosing interruptions of any study drug are permitted for reasons not related to study treatment (for example, minor surgery, unrelated medical events, patient vacation, and/or holidays). The reason for interruption should be documented on the CRF.

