9.1 Discontinuation from Study Treatment

Patients will be discontinued from study treatment in the following circumstances:

- the patient is enrolled in any other clinical trial involving an investigational product or any other type of medical research judged not to be scientifically or medically compatible with this study
- the patient becomes pregnant during the study
- the patient is significantly noncompliant with study procedures and/or treatment
- disease progression

- If a patient is clinically stable at the first radiologic progressive disease by RECIST v1.1 (Eisenhauer et al. 2009), the patient may be considered for continuation on the study until progression is confirmed. For patients to be considered for continuation the following criteria must all be met, and after consultation with the Principal Investigator:
 - Absence of symptoms and signs indicating clinically significant progression of disease
 - No decline in ECOG performance status
 - Absence of symptomatic rapid disease progression requiring urgent medical intervention (e.g. symptomatic pleural effusion, spinal cord compression).
- Treatment beyond progression must not delay an imminent intervention to prevent serious complications of disease progression (e.g., central nervous system metastases).
- Subjects' clinical data must be available for CRF source verification. Copies of tumor images must be made available for review by the sponsor or its designee upon request.
- unacceptable toxicity
- the patient, for any reason, requires treatment with another therapeutic agent that has been demonstrated to be effective for treatment of the study indication. Discontinuation from study treatment will occur prior to introduction of the new agent.
- the investigator decides that the patient should be discontinued from study treatment
- the patient requests to be discontinued from study treatment
- the patient's designee (for example, parents, legal guardian, or caregiver) requests that the patient be discontinued from study treatment

Patients are considered to have discontinued from study treatment when all study treatments are no longer administered. Based on investigator discretion and/or patient preference, patients may continue on study treatment while taking either LY3214996 or abemaciclib alone. Patients who are discontinued from study treatment will have follow-up procedures performed as shown in the Schedule of Activities (Section 2).

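### Appendix 4's baseline-grading footnote also moves the combined AST/ALT–bilirubin stop to above 3 × baseline, leaving a gap in a safety rule that one added sentence would close

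*Combined protocol and SAP*

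**What the plan says.** The AST/ALT table in Appendix 4 grades elevations on printed multiples of ULN: up to 3.0 for Grade 1, above 3.0 to 5.0 for Grade 2, above 5.0 to 20.0 for Grade 3, and above 20.0 for Grade 4. The footnote marker sits on the table header, so the footnote applies to every row: "Use ULN unless baseline is greater than ULN, then use baseline for grading".

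The lowest row, labeled "Grade 1 (>ULN-3.0x ULN", asks for no dose change and has no bilirubin condition. A first Grade 2 elevation without the bilirubin rise leads to a hold and resumption at the same dose. The row "Grade 2 (with increase in total bili > 2x ULN" discontinues both drugs, as does the matching Grade 3 row. The bilirubin limit stays in multiples of ULN.

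The paragraph above the table recommends holding therapy from Grade 2 and adds: "Please follow AST, ALT, and total bilirubin at least weekly until" recovery to Grade 1 or below. It also says: "Liver function can be monitored more frequently per investigator discretion".

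Section 6.1, item 8, admits AST and ALT up to 2.5 × ULN, or 5 × ULN with liver tumor. Entry bilirubin is capped at 1.5 × ULN, or 2.0 mg/dL in Gilbert's disease.

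**The concern.** The table treats AST/ALT elevation with a bilirubin rise as a different order of event from AST/ALT elevation alone: permanent discontinuation instead of hold and resume. Because that stop is defined by grade, moving the grading reference to baseline moves the stop too. A raised AST/ALT at entry is a good reason not to react to the same AST/ALT value later. It is not a reason to discount a new bilirubin rise, and entry bilirubin was capped.

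At stake is whether a patient who entered above ULN, and then has both AST/ALT and bilirubin rise, meets a defined action or depends on interpretation. The appendix itself names hepatotoxicity as a known adverse reaction of abemaciclib. The weekly liver tests are also tied to Grade 2, so they are delayed by the same footnote.

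**Working it through.** **Inputs.** Grade multipliers 3.0, 5.0 and 20.0, the footnote, and the bilirubin limit of 2 × ULN (Appendix 4); entry limits (Section 6.1, item 8). I assume that the printed multiples apply to baseline, since the footnote gives no others. The protocol does not say whether baseline means screening or Cycle 1 Day 1.

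**Formula.** Threshold in units of ULN = multiplier × max(1, b), where b is baseline divided by ULN.

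**Reproducing the table.** With b = 1 this returns 3.0, 5.0 and 20.0 × ULN, as printed. The combined stop then starts above 3.0 × ULN.

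**Raised baselines.** The combined stop starts above 3 × b. The affected rises run from max(3, b) up to 3 × b. The last column requires a rise to at least 1.5 × baseline, an assumed margin that excludes trivial changes. Its lower end is max(3, 1.5 × b).

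| Baseline (× ULN) | Stop starts above | Lower end, any rise | Lower end, 1.5-fold margin |
|---|---|---|---|
| 1.5 | 4.5 | 3 | 3 |
| 2.5 | 7.5 | 3 | 3.75 |
| 3 | 9 | 3 | 4.5 |
| 4 | 12 | 4 | 6 |
| 5 | 15 | 5 | 7.5 |

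Baselines above 2.5 require liver tumor. Without a margin, the lower end for baselines of 3, 4 and 5 would count rises of barely more than 1.0-fold, so the last column is the fairer description.

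**Example without liver tumor.** Baseline 2.5, AST/ALT 7 × ULN, bilirubin newly above 2 × ULN.
- On the printed ULN scale, 7 lies between 5.0 and 20.0: Grade 3 with bilirubin, so both drugs are discontinued.
- On the footnote, 7 / 2.5 = 2.8 × baseline: Grade 1 or below, no dose change.
- The example holds for any baseline of at least 7 / 3 = 2.33 × ULN.

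**Limit of the effect.** A value of 14 × ULN escapes the stop only from baselines of 14 / 3 = 4.67 up to 5. From 2.5 it is 14 / 2.5 = 5.6 × baseline, Grade 3, and the stop applies.

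**Bilirubin.** Above 2 × ULN is more than 2.0 / 1.5 = 1.33 times the entry cap, so it is normally a new rise. In Gilbert's disease the 2.0 mg/dL cap is 2.0 / 1.3 = 1.54 to 2.0 / 1.0 = 2.0 × ULN, for an assumed ULN of 1.3 to 1.0 mg/dL. The condition therefore needs the word *newly*.

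**What else could act in the gap.**
- *Appendix 4, general rule for toxicities not listed.* If bilirubin counts as unlisted, Grade 3 or 4, or intolerable Grade 2, leads to a hold and then resumption one level lower. Tolerable Grade 2 gets no reduction.
- *Section 8.3.* Patients with drug-related toxicity not recovered to "grade 1 within 3 weeks will be discontinued". AST/ALT graded on baseline is already at Grade 1 or below, so this can act only through bilirubin.
- *Section 9.1.* "unacceptable toxicity" is listed, and so is the case where "the investigator decides that the patient should be discontinued from study treatment". Neither has a threshold.
- *Sections 12, 13 and 13.1.* Documented laboratory review, weekly review meetings and notification of the monitoring committee chair provide oversight, again without a threshold.

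**The case against.** The strongest defense is that the table is internally consistent: the rows are written by grade and the footnote defines the grade. Patients with liver tumor may enter at 5 × ULN, already the top of printed Grade 2, so some baseline adjustment is unavoidable. Where to set a combined threshold in such patients is a medical judgment. This stands. It is why the ordinary rows should be kept, and why the margin proposed here is only an example for the medical team to confirm.

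A second objection is that asking for no dose change on AST/ALT grade does not forbid action on bilirubin. Appendix 4 has no row for bilirubin alone, so the general rule for unlisted toxicities is a natural reading. This also largely stands. A reader might infer that the protocol directs continued dosing through developing liver injury. The documents do not support that, because the provisions above leave room to hold or stop. What they lack is a defined, immediate combined action. Bilirubin grade limits are not printed, so the width of the remaining gap cannot be fixed exactly.

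Two further inferences are tempting and should not be drawn:
- **Phase 1 evidence.** The one dose-limiting toxicity among 6 evaluable patients at this dose was Grade 3 ALT/AST (Table 3.1), but its baseline and bilirubin are not stated. The 3 of 20 patients with raised ALT in Part C (Table 3.2) are not separated by dose level. Neither table reports a combined event, so neither measures this gap.
- **Visit schedule.** Routine chemistry is every 28 days from cycle 3, against the 3-week limit in Section 8.3. The first is a scheduling minimum and the second a recovery limit. They would differ without the footnote.

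**Conclusion.** The point holds as a cheap improvement. For patients who enter with AST/ALT above ULN, the combined stop begins above 3 × baseline, which is up to 7.5 × ULN without liver tumor and up to 15 × ULN with it, while bilirubin stays at 2 × ULN. Those two figures are the extremes at the entry limits; smaller raised baselines give smaller shifts. Below the shifted level, any hold depends on how the general Appendix 4 rule is read, on the Section 8.3 limit acting through bilirubin, or on judgment.

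This is a gap in a safety rule. It is not a demonstrated harm, and it does not show that baseline grading is wrong. The number of patients affected cannot be estimated from the documents. The Investigator's Brochure to which the appendix refers was not available, so any guidance there is not taken into account. The conclusion rests on reading the header marker as covering every row and on applying the printed multiples to baseline.

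**What to change.** Keep the footnote and leave the existing discontinuation rows unchanged. Add the following, only for patients with baseline AST/ALT above ULN whose value is still at or below 3 × baseline:

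*If AST or ALT is > 3 × ULN and has risen meaningfully above baseline (for example to at least 1.5 × baseline, an assumed value for the medical team to confirm), with total bilirubin newly > 2 × ULN, hold both drugs and check AST, ALT and bilirubin at least weekly; discontinue unless the rise is attributed to tumor progression or another non-drug cause under the Section 8.3 attribution step.*

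Restricting the scope this way matters. Patients already covered by a discontinuation row gain no new exception, and the attribution step is the one the protocol already uses.

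The cost is one sentence in one table. AST, ALT and total bilirubin are already in the scheduled metabolic profile, and only the few patients who meet the condition need extra weekly tests. The downside is that some patients with liver metastases will be held or stopped earlier than now. A patient whose AST/ALT has stayed at its entry level is unaffected.
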